#### Aim 2: Retrospective chart review

1. Estimated number of records to be reviewed: 500/year
2. Criteria for inclusion/exclusion: Women with a history of GDM who had an OGTT 6-8 weeks post-partum as part of standard of care at Yale Medicine's Maternal-Fetal Medicine Clinic in the past 3 years and throughout the duration of this study. (May 1,2016 until April 30, 2024)
3. Information collected and recorded from medical records:
  - a. Data to be recorded from the chart:
    - i. MRN
    - ii. Sociodemographic information (age, race/ethnicity, preferred language, marital status, insurance, tobacco use)
    - iii. Pre-pregnancy height/weight/BMI
    - iv. GDM history (date of diagnosis, management)
    - v. Date of delivery and delivery method
    - vi. Weight/BMI on day of delivery
    - vii. Gravida and parity
    - viii. Date of OGTT during pregnancy and post-partum
    - ix. OGTT lab results (during pregnancy and post-partum)
    - x. Weight/BMI on day of OGTT (during pregnancy and post-partum)
    - xi. Infant feeding practices
    - xii. Infant birth weight/percentile and weight/percentile at 2 months of age

- b. Type of medium that will be used to record the information and the plans for maintaining confidentiality and security of the data: CSV file. The file will be stored on a secured server on an encrypted laptop and/or computer that is stored in a locked office.
- c. Who will have access to the data, and how access to the data storage (whether paper-based or electronic) will be monitored: All data will be available to study personnel and stored on a secured server on an encrypted laptop and/or computer that is stored in a locked office.

4. How will the data and/or identifiers be destroyed when no longer needed for research purposes? If it will not please explain why data must be retained, for how long and how it will be kept secured: All data comes from the EPIC EMR and therefore cannot be destroyed and will be retained indefinitely. All de-identified data will be stored on a secured server on an encrypted laptop and/or computer that is stored in a locked office.

5. Genetic Testing      N/A

6. **Subject Population:** Provide a detailed description of the types of human subjects who will be recruited into this study.

Aim 1:

- Group 1: 16 women (ages 18-45, HbA1C < 6.5%) with a history of GDM who exclusively or mostly breast-fed (< 6 ounces of formula/24 hours at 6-9 weeks of delivery) for at least 4-6 months and who delivered within the past 18 months
- Group 2: 16 women (ages 18-45, HbA1C < 6.5%) with a history of GDM who exclusively or mostly formula-fed (no breastfeeding or < 3 weeks of breastfeeding) and who delivered within the past 18 months

7. **Subject classification:** Check off all classifications of subjects that will be specifically recruited for enrollment in the research project. Will subjects who may require additional safeguards or other considerations be enrolled in the study? If so, identify the population of subjects requiring special safeguards and provide a justification for their involvement.

 Children	 Healthy	 Fetal material, placenta, or dead fetus
 Non-English Speaking	 Prisoners	 Economically disadvantaged persons
 Decisionally Impaired	 Employees	 Pregnant women and/or fetuses
 Yale Students	 Females of childbearing potential	

NOTE: Is this research proposal designed to enroll children who are wards of the state as potential subjects?

Yes  No

8. **Inclusion/Exclusion Criteria:** What are the criteria used to determine subject inclusion or exclusion?

Aim 1:

Inclusion Criteria:

- Women between the ages of 18-45 with a history of GDM (as defined as the American Diabetes Association criteria) who delivered a singleton, live birth at  $\geq$  35 weeks gestation within the past 18 months
- HbA1C < 6.5% at time of screening
- Delivery within the past 18 months
- Group 1: exclusively or mostly breast-fed (< 6 ounces of formula/24 hours at 6-9 weeks of delivery) for at least 4-6 months

Exclusion criteria:

- Currently lactating or lactation within the past 1 month at the time of the screening visit
- Diagnosis of diabetes (T1D or T2D) prior to pregnancy
- Current use of any glucose-lowering agents
- Pregnancy related medical problems including preeclampsia
- Major congenital fetal anomalies
- Creatinine > 1.5mg/dL, Hematocrit < 35%, ALT and AST > 2.5X upper limit of normal
- Known psychiatric disorders, alcohol abuse, HIV, hepatitis, renal disease, hepatic disease, untreated heart disease, untreated thyroid disease, active systemic infection or malignancy
- Illicit drug use (by the participant's self-report)
- History of post-partum depression
- Use of weight loss supplements or dieting 6 months prior to study
- Corticosteroid or opiate use within 6 months of study

9. How will **eligibility** be determined, and by whom?

Eligibility will be determined by a qualified physician or nurse practitioner associated with the research protocol and will be based upon the above inclusion/exclusion criteria.

10. **Risks:** Describe the reasonably foreseeable risks, including risks to subject privacy, discomforts, or inconveniences associated with subjects participating in the research.

Physical examination, venipuncture/IV placement, lab data collection and analysis: Subjects will receive a comprehensive medical history assessment, physical examination and lab testing to ensure good physical health status and eligibility. These are routine medical procedures and should add no risks other than those normally associated with these procedures. Study doctors and/or nurse practitioners will assess the screening laboratory blood work and if any abnormal findings occur, they will provide appropriate medical advice. Potential participants who are excluded from the study due to medical reasons, or those who are in immediate need for medical or psychiatric attention, will be referred to the appropriate facilities at Yale New Haven Hospital. Subjects will be exposed to the risk of venipuncture/IV placement that is routinely done in the HRU and CSRU. Risks associated include: local bruising, hematoma, or infection. If this occurs, appropriate treatment will be provided immediately. On extremely rare occasions, a blood clot or infection might occur, and if this occurs, subjects will be treated at the HRU or CSRU, which is fully staffed with nursing specialists and medical personnel. These risks are mitigated by the use of research nurses who have extensive experience in venipuncture and IV catheterization. Transient vasovagal symptoms, e.g. nausea, sweating, and lightheadedness may also occur during IV catheter placement.

Oral glucose tolerance test (OGTT): The OGTT is a commonly used outpatient test for diagnosis of type 2 diabetes and gestational diabetes. It is not associated with any specific adverse effects. Occasionally, some patients may experience mild nausea or GI discomfort following drinking the 75-gram glucose drink; however, this typically resolves after eating food.

Hyperinsulinemic-euglycemic clamp: The infusion of insulin and glucose poses a small risk that plasma glucose will fall below the predetermined level (90-100 mg/dL) resulting in little or no symptoms of hypoglycemia: sleepiness, hunger, anxiety, diaphoresis and tremor exaggerated symptoms. These symptoms are quickly reversed with IV dextrose infusion. The risks of drawing blood and inserting an IV line are detailed above. The studies will be performed under the supervision of a qualified physician or nurse practitioner. All solutions that are administered via IV will be sterile, pyrogen free, and prepared in a sterile environment. During glucose infusion, D20 (20% glucose) will be used to decrease the risk of thrombophlebitis that is associated

with hypertonic glucose solutions. To avoid hypoglycemia during the hyperinsulinemic clamp, plasma glucose will be checked every five minutes using a bedside glucose monitor. Based on these measurements, the plasma glucose will be adjusted via the D20 infusion.

Phlebotomy: The total amount of blood drawn for this study is 220 mL (including screening, OGTT and hyperinsulinemic-euglycemic clamp). People who are in good health are not usually affected by this kind of blood loss. However, to be safe, subjects will be warned against donating blood for at least 6 weeks before and after completing this study. Additionally, subjects are screened for anemia at the first visit and women with a hematocrit less than 35% will be excluded.

6,6D2-glucose and D5-glycerol: The infusion of 6,6D2-glucose and D5-glycerol involves no radioactivity, and the glucose and glycerol are metabolized just as the unlabeled metabolite. Clinical research studies using these tracers have been used at Yale for decades with no adverse effects. The isotopes are purchased from Cambridge Isotopes, Inc. in powder form which has been certified to be sterile and free of pyrogens. The tracers are made into a solution by the Yale New Haven Hospital Investigational Drug Service (IDS). The solutions are tested to be free of pyrogens and to be sterile before being administered. All certifications are kept with the IDS.

Continuous glucose monitoring (CGM): The CGM poses no major risks to the subjects. Participants may feel a mild discomfort (pin prick sensation) during the sensor insertion. Some individuals may experience bruising of the skin at the insertion site of the CGM sensor, which resolves by itself in a few days. Redness and discomfort (inflammation) can occur at the sensor insertion site. Some individuals may be sensitive to the adhesive that keeps the sensor attached to the skin. If the participant notices significant skin irritation around or under the sensor, they will be instructed to contact us and it can be removed. Rarely sensors may fracture and a small piece may remain under the skin which will need to be removed by a study physician. This may cause mild discomfort, bruising, or temporary bleeding. The participants will also be informed that the sensor must be removed before an MRI, a CT scan, or diathermy treatment.

DXA scanning: DXA scanning for body composition is performed routinely by our group. The DXA measurement poses no major risk to the subject. The amount of radiation the subject will be exposed to is small and is one tenth of the amount of radiation for a chest X-ray.

Indirect calorimetry: Indirect calorimetry is routinely performed by our research team and poses no major risks to the users. Some people may feel claustrophobic and if this happens, we will remove the hood and stop the testing.

Questionnaires: The questionnaires are generally benign in nature. The major inconvenience is the time taken to complete them and a possible breach of confidentiality.

**11. Minimizing Risks:** Describe the manner in which the above-mentioned risks will be minimized.

IV Insertion and Blood Drawing: Risks of bruising, clotting, and infection will be minimized by having venipuncture performed by trained, experienced personnel under sterile conditions. To avoid injury due to fainting, the antecubital vein catheter will be inserted when the subjects are recumbent. All infused solutions will be prepared in sterile form by the YNHH Investigational Drug Services (IDS) pharmacy and tested for pyrogenicity and sterility before use. During studies 20% dextrose will be used to reduce the risk of thrombophlebitis associated with use of excessively hypertonic glucose solutions (50% dextrose). Women with a hematocrit less than 35% will be excluded. Patients will be advised to refrain from blood donation for 6 weeks after study completion.

Hyperinsulinemic-euglycemic clamp: The infusion of insulin and glucose poses a small risk that plasma glucose will fall below the predetermined level (90-100 mg/dl) resulting in hypoglycemia, which can be quickly reversed with IV dextrose infusion. To avoid hypoglycemia during the clamp, plasma glucose will be checked every five minutes using a bedside glucose monitor. Based on these measurements, the plasma glucose will be adjusted via the dextrose infusion. The risks of drawing blood and inserting an IV line are detailed above. The studies will be performed under the supervision of a qualified physician or nurse practitioner. All solutions that are administered via IV will be sterile, pyrogen free, and prepared in a sterile environment. During glucose infusion, dextrose 20 (20% glucose) will be used to decrease the risk of thrombophlebitis that is associated with hypertonic glucose solutions (50% glucose).

6,6D2-glucose and D5-glycerol: The infusion of 6,6D2-glucose and D5-glycerol involves no radioactivity, and the glucose and glycerol are metabolized just as the unlabeled metabolites. Clinical research studies using these tracers have been used at Yale for decades with no adverse effects. The isotopes are purchased from (Cambridge Isotopes, Inc.) in powder form which has been certified to be sterile and free of pyrogens. They are made into a solution by the YNHH IDS. The solutions are tested to be free of pyrogens and to be sterile before being administered to the participants. All certifications are kept with the IDS.

Continuous glucose monitoring (CGM): CGM catheter will be placed under sterile conditions by experienced staff members. In case of signs of irritation, inflammation or bruising at the sensor insertion site, the sensor will need to be removed immediately and standard care will be applied. The participants will be given one of the study physician or nurse practitioner's cell phone number to contact for any questions, concerns or problems.

Questionnaires: The major inconvenience of the questionnaires is the time taken to complete them and a possible breach of confidentiality. Study participation is voluntary, and subjects are informed that they are free to withdraw at any time without penalty. All data will be kept confidential except in cases of imminent danger to the participants. Such limits to confidentiality will be clearly explained to participants verbally and in the written consent forms. Good clinical and research practice procedures and HIPAA regulations will be followed. No subjects are identified by name in any of the published literature and only by code in major data storage areas.

12. **Data and Safety Monitoring Plan:** Include an appropriate Data and Safety Monitoring Plan (DSMP) based on the investigator's risk assessment stated below. (Note: the HIC will make the final determination of the risk to subjects.)
  - a. What is the investigator's assessment of the overall risk level for subjects participating in this study? We feel that the risks associated with the study proposed should be deemed as moderate, for the following reasons:
    - 1) We do not view the risks associated with the hyperinsulinemic-euglycemic clamp and glycerol infusion technique as minimal.
    - 2) Given the established safety and validity of these clamp techniques, we do not view the proposed studies as high risk.
  - b. If children are involved, what is the investigator's assessment of the overall risk level for the children participating in this study? N/A
  - c. Include an appropriate Data and Safety Monitoring Plan. Examples of DSMPs are available here <http://your.yale.edu/policies-procedures/forms/420-fr-01-data-and-safety-monitoring-plans-templates> for
    - i. Minimal risk

ii. Greater than minimal

d. For multi-site studies for which the Yale PI serves as the lead investigator: N/A

**Greater Than Minimal**  
**RiskDSMP**

**1. Personnel responsible for the safety review and its frequency:**

The principal investigator will be responsible for monitoring the data, assuring protocol compliance, and conducting the safety reviews at the specified frequency, which must be conducted at a minimum of every 6 months (including when reapproval of the protocol is sought). During the review process, the principal investigator (monitor) will evaluate whether the study should continue unchanged, require modification/amendment, or close to enrollment. Either the principal investigator or the IRB have the authority to stop or suspend the study or require modifications.

**2. The risks associated with the current study are deemed greater than minimal for the following reasons:**

1. We do not view the risks associated with phlebotomy, hyperinsulinemic-euglycemic clamp and glycerol infusion as minimal risks.

Although we have assessed the proposed study as one of greater than minimal risk, the potential exists for anticipated and/or unanticipated adverse events, serious or otherwise, to occur since it is not possible to predict with certainty the absolute risk in any given individual or in advance of first-hand experience with the proposed study methods. Therefore, we provide a plan for monitoring the data and safety of the proposed study as follows:

**3. Attribution of Adverse Events:**

Adverse events will be monitored for each subject participating in the study and attributed to the study procedures / design by the principal investigator according to the following categories:

- a.) Definite: Adverse event is clearly related to investigational procedures(s)/agent(s).
- b.) Probable: Adverse event is likely related to investigational procedures(s)/agent(s).
- c.) Possible: Adverse event may be related to investigational procedures(s)/agent(s).
- d.) Unlikely: Adverse event is likely not to be related to the investigational procedures(s)/agent(s).
- e.) Unrelated: Adverse event is clearly not related to investigational procedures(s)/agent(s).

**4. Plan for Grading Adverse Events:**

The following scale will be used in grading the severity of adverse events noted during the study:

- 1. Mild adverse event
- 2. Moderate adverse event
- 3. Severe

**5. Plan for Determining Seriousness of Adverse Events:**

Serious Adverse Events:

In addition to grading the adverse event, the PI will determine whether the adverse event meets the criteria for a Serious Adverse Event (SAE). An adverse event is considered serious if it results in any of the following outcomes:

1. Death;
2. A life-threatening experience in-patient hospitalization or prolongation of existing hospitalization;
3. A persistent or significant disability or incapacity;
4. A congenital anomaly or birth defect; OR
5. Any other adverse event that, based upon appropriate medical judgment, may jeopardize the subject's health and may require medical or surgical intervention to prevent one of the other outcomes listed in this definition.

An adverse event may be graded as severe but still not meet the criteria for a Serious Adverse Event.

Similarly, an adverse event may be graded as moderate but still meet the criteria for an SAE. It is important for the PI to consider the grade of the event as well as its "seriousness" when determining whether reporting to the IRB is necessary.

## 6. Plan for reporting UPIRSOs (including Adverse Events) to the IRB

The principal investigator will report the following types of events to the IRB:

Any incident, experience or outcome that meets ALL 3 of the following criteria:

1. Is unexpected (in terms of nature, specificity, severity, or frequency) given (a) the research procedures described in the protocol-related documents, such as the IRB-approved protocol and informed consent document and (b) the characteristics of the subject population being studied; AND
2. Is related or possibly related to participation in the research (*possibly related* means there is a reasonable possibility that the incident, experience, or outcome may have been caused by the procedures involved in the research); AND
3. Suggests that the research places subjects or others at greater risk of harm (including physical, psychological, economic, legal, or social harm) than was previously known or recognized.

Unanticipated Problems Involving Risks to Subjects or Others (UPIRSOs) may be medical or non-medical in nature, and include – but are not limited to – *serious, unexpected, and related adverse events* and *unanticipated adverse device effects*. **Please note** that adverse events are reportable to the IRB as UPIRSOs **only** if they meet all 3 criteria listed above.

These UPIRSOs/SAEs will be reported to the IRB in accordance with IRB Policy 710, using the appropriate forms found on the website. All related events involving risk but not meeting the *prompt* reporting requirements described in IRB Policy 710 should be reported to the IRB in summary form at the time of continuing review. If appropriate, such summary may be a simple brief statement that events have occurred at the expected frequency and level of severity as previously documented. In lieu of a summary of external events, a current DSMB report can be submitted for research studies that are subject to oversight by a DSMB (or other monitoring entity that is monitoring the study on behalf of an industry sponsor).

### 13. Statistical Considerations: Describe the statistical analyses that support the study design.

Group sample sizes of 15 and 15 achieve 80% power to detect a between-group difference of 0.61 in a design with 7 repeated measurements (taken at time 0, 5, 10, 30, 60, 90, 120 min) having a autoregressive AR(1)

covariance structure when the standard deviation is 1, the correlation between observations on the same subject is 0.6, and the alpha level is 0.05. To account for up to 5-10% missing data due to drop out or poor quality data, we will need to enroll a total of 32 subjects (16 per group) for this study. Data Analysis: Primary endpoints: Whole body insulin sensitivity, endogenous glucose production, whole body lipid turnover rates. Secondary endpoints: Plasma NEFA, TGs, insulin levels, metrics of body composition. Statistical Analysis: Before statistical testing, all continuous variables will be tested for normality of distribution. Summary statistics will be computed. For between-group comparisons of patient characteristics, two sample t-test or Mann-Whitney U test will be used for continuous variables, and Fisher's exact test for categorical variables. Comparisons of repeatedly measured glucose and lipid turnover rates will be made using the mixed model analysis. Fixed factors include group and time and their interactions. A random effect for subject plus an autoregressive covariance matrix will be used to accommodate within-subject correlation of repeated assessments. Linear contrasts comparing differences between groups or different time points within a group will be estimated.

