**SECTION I: RESEARCH PLAN**

1. **Statement of Purpose:** State the scientific aim(s) of the study, or the hypotheses to be tested.

Aim 1: Does lactation improve insulin sensitivity and increase lipolysis in women?

In this Aim, we will assess whether lactation amongst women with a history of GDM will improve whole body insulin sensitivity as well as increase whole body lipid turnover by using hyperinsulinemic-euglycemic clamps combined with [6,6-2H]-glucose and [2H5]-glycerol infusions. These stable, non-radiating isotopes have been used extensively and safely to study the mechanisms of insulin resistance amongst non-pregnant as well as pregnant humans; however, these techniques have not previously been applied to the study of insulin sensitivity during lactation. Our goals will be two-fold: 1) to determine whether lactation induces similar changes in insulin sensitivity in humans as in mice and 2) to pilot the feasibility of performing larger, more detailed metabolic studies in this population of women post-partum.

Aim 2: Retrospective chart review of women with a history of GDM who had an OGTT 6-8 weeks post-partum as part of standard of care at Yale Medicine's Maternal-Fetal Medicine Clinic.

2. **Probable Duration of Project:** State the expected duration of the project, including all follow-up and data analysis activities.

5 years

3. **Background:** Describe the background information that led to the plan for this project. Provide references to support the expectation of obtaining useful scientific data.

Our premise is that lactation protects against the development of Type 2 Diabetes Mellitus (T2D) by mobilizing tissue triglycerides (TGs) and fully reversing the insulin resistance (IR) of pregnancy. A growing body of epidemiological data has indicated that nursing protects against T2D in all women but particularly amongst women with gestational diabetes mellitus (GDM) (1-8). However, no studies have investigated the detailed molecular mechanisms underlying these beneficial effects of lactation. Many studies have

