Screening visit (Visit 1): For women who did not attend the post-partum OGTT visit or who are not patients at the MFM Clinic, they will be consented at this visit. All participants will be screened at the YNHH Research Unit (HRU) or Church Street Research Unit (CSRU) with a medical history and exam. Blood will be collected for HbA1C, Cr, ALT, AST, TSH, hematocrit and fasting lipid panel, and a urine pregnancy test will be administered. Oral glucose tolerance tests (OGTT) will be performed after an overnight fast. A nurse will insert an intravenous (IV) catheter and subjects will ingest 7.5 oz of glucola, which contains 75 g of glucose in flavored water. Blood samples will be taken at certain time points before and after glucola ingestion for the measurement of plasma glucose and insulin concentrations. Approximately 60 mL of blood will be drawn at this visit.

Continuous glucose monitor (CGM) placement (Visit 2): For up to 10 days prior to Visit 3, eligible participants will be asked to wear a CGM (Dexcom G6 Pro). At the visit for CGM placement (either at CSRU or HRU): 1) a trained study staff member will explain to the participant how to use the CGM, and 2) a trained study staff member will insert the CGM's plastic wire-like tip under the participant's skin with the use of the CGM applicator. This visit will take approximately 15 minutes.

The CGM consists of a sensor that measures glucose levels from the interstitial tissue. A transmitter that captures and stores data from sensor. The sensor is sterile and comes in an unopened package. Each sensor and transmitter are single use only and disposable. The Dexcom G6 Pro does not require any calibration. This means that no finger sticks are required for its use. Participants will need to return the sensor within 30 days of sensor placement.

The Dexcom G6 Pro data is blinded to study participants. Study staff will explain to the participants that intense exercise may cause the sensor to loosen due to sweat or movement of the sensor. If the CGM sensor/transmitter falls off while the participant is wearing it, we will ask them to return to the HRU or CSRU so that a new sensor/transmitter can be re-inserted. Subjects will be provided with our contact information in the event that they have any questions, concerns or issues related to the CGM.

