After completing the 10-day CGM session, the sensor will be removed by a trained study staff member. To remove the sensor, the adhesive patch will be gently peeled off from the skin. Removal of the sensor is a painless procedure. The sensor/transmitter will be discarded after use. CGM removal will occur during Visit 3.

Hyperinsulinemic-euglycemic clamp (Visit 3): After an overnight fast, eligible subjects will return to the YNHH HRU. Two IV catheters will be inserted: one into a distal arm or hand vein that will be placed in a heated box to allow for the sampling of arterialized venous blood; the second into an antecubital vein for administration of a primed (200 mg/m^2) and continuous infusion of [6,6-2H] Glucose and [2H5] Glycerol

(non-radioactive stable isotopes) as well as for collecting blood samples for insulin and glucose measurements. After an equilibration period lasting 2 hours., the 2-step euglycemic-hyperinsulinemic clamp study will be performed. A primed-continuous infusion of regular insulin will be given at 8 mU/(m^2 × min) during the first 2 hours, and increased to 40 mU/(m^2 × min) for the subsequent 2 hours. Plasma glucose levels will be measured every 5 min, and a variable glucose infusion will be initiated to maintain levels at ~90 mg/dl. Plasma samples will be drawn at baseline and throughout the infusion period for measurement of isotope enrichment, insulin, NEFA, glycerol turnover, and additional hormones which may be altered with lactation. Approximately 160 mL of blood will be drawn at this visit.

Also at this visit, we will perform indirect calorimetry a total of 3 times (once before and twice during the insulin clamp). A transparent plastic hood will be placed over the participant's head for 30 minutes each time. A hose connects the hood to a calorimeter, which measures oxygen consumption and carbon dioxide production and calculates resting energy expenditure.

After the insulin clamp is completed, body composition will be assessed using whole body DXA. The DXA scan will be performed in the HRU to measure fat distribution, body fat, lean body mass and bone density.

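### The stated 80% power at 0.61 SD reproduces as a one-sided test that the plan does not declare; two-sided, with 0.6 between neighbouring values, it is about 70%

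*Combined protocol and SAP*

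**What the plan says.** Section I, item 13 holds the only power calculation. It gives 15 analysable women per group, 80% power, a between-group difference of 0.61, a standard deviation of 1 and an AR(1) covariance in "a design with 7 repeated measurements (taken at time 0, 5, 10, 30, 60, 90, 120 min"). It adds that "the correlation between observations on the same subject is 0.6, and the alpha level is 0.05". It does not say whether alpha is one- or two-sided, over what gap the 0.6 applies, or which variable the 0.61 belongs to. Enrolment of 32 (16 per group) follows from it.

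The same item then lists "Primary endpoints: Whole body insulin sensitivity, endogenous glucose production, whole body lipid turnover rates", with no effect size, SD or power attached to any of them. On analysis it says: "Comparisons of repeatedly measured glucose and lipid turnover rates will be made using the mixed model analysis", with an autoregressive covariance. Insulin sensitivity is not named in that sentence.

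Aim 1 (Section I, item 1) asks a directional question: "Does lactation improve insulin sensitivity and increase lipolysis in women". No passage turns that into a one-sided test.

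The Research Plan (Section I, item 4) lists no times that would identify the seven-point grid. For the OGTT, "Blood samples will be taken at certain time points before and after glucola ingestion". For the clamp, "Plasma samples will be drawn at baseline and throughout the infusion period", and the only interval given is for plasma glucose, every 5 minutes.

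**The concern.** When alpha is given as 0.05 without qualification and group differences are to be estimated, most readers assume a two-sided test. When an AR(1) correlation is given as a single number, they take it as the correlation between neighbouring values. Under those two ordinary readings the stated inputs do not give 80%. They give about 70%, so the chance of missing a true 0.61 SD difference is about 30% rather than 20%.

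This matters because the figure is the sole justification for 32 women, and because a null result will be read against it. Nor can a reader tell which primary endpoint the sensitivity of 0.61 SD belongs to.

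**Working it through.** **Inputs (all from Section I, item 13).** n = 15 per group; difference 0.61; SD 1 per measurement; seven values; AR(1), correlation 0.6; alpha 0.05. Inferred, not stated: the comparison is of each woman's unweighted mean over the seven values.

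**Step 1. Variance of the seven-value mean, 0.6 between neighbouring values.**

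v = [7 + 2 × Σ(7 − k) × 0.6^k, k = 1 to 6] / 49

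The six terms are 3.600, 1.800, 0.864, 0.389, 0.156 and 0.047, sum 6.855. So v = (7 + 13.710)/49 = 0.4227, and the SD of the mean is √0.4227 = 0.650.

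**Step 2. Reproduce the plan's figure.** SE = √(2 × 0.4227/15) = 0.2374. Noncentrality = 0.61/0.2374 = 2.57, with 28 df. Noncentral t:

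| Test | Critical t | Power at 0.61 SD | Difference for 80% power | Smallest n per group for 80% at 0.61 SD |
|---|---|---|---|---|
| One-sided 0.05 | 1.701 | 80.6% | 0.605 SD | 15 (14 gives 78.0%) |
| Two-sided 0.05 | 2.048 | 69.9% | 0.689 SD | 19 (18 gives 78.1%) |

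The one-sided row matches the plan on both power and n, and its 0.605 rounds to 0.61. This suggests a one-sided calculation, but the documents do not say so. With all 16 enrolled women per group analysed, two-sided power is 72.8%.

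**Step 3. Does the method of calculation explain the gap?** The GLS variance, 1/(1′R⁻¹1), is 0.400.

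| Method | Two-sided | One-sided |
|---|---|---|
| Unweighted mean, t | 69.9% | 80.6% |
| Unweighted mean, normal | 72.9% | 82.2% |
| GLS weights, t | 72.2% | 82.4% |
| GLS weights, normal | 75.2% | 84.1% |

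No two-sided variant with 0.6 between neighbouring values reaches 80%.

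**Step 4. Does the uneven spacing explain it?** The gaps are 5, 5, 20, 30, 30 and 30 minutes, on average 20. Suppose instead that the correlation decays with clock time as 0.6^(gap/lag). Unweighted mean, t test:

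| 0.6 applies per | v | Two-sided | One-sided |
|---|---|---|---|
| 5 min | 0.223 | 92.7% | 96.4% |
| 10 min | 0.306 | 83.1% | 90.4% |
| 12 min | 0.336 | 79.4% | 87.8% |
| 20 min | 0.441 | 68.1% | 79.1% |
| 30 min | 0.538 | 59.4% | 71.8% |

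Two-sided power is exactly 80% at a lag of 11.7 minutes (about 13 by the normal formula). One-sided it is 80% at 19.0 minutes.

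**Step 5. Insulin sensitivity, if analysed as one value per woman (assumption).** In units of the between-woman SD of that summary, SE = √(2/15) = 0.3651. The difference detectable with 80% power is 1.06 SD two-sided and 0.93 SD one-sided. To compare this with the plan's target, 0.61 must first be put in the same kind of unit: 0.61/0.650 = 0.94 SD of the seven-value mean.

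**The case against.** **The 80% is not wrong on every reading.** This stands. It reproduces one-sided with 0.6 between neighbouring values, and two-sided if 0.6 applies at a short lag; at 5 or 10 minutes the plan would even be conservative. The directional wording of Aim 1 could be offered in support of a one-sided test. But neither condition is declared, and the figure depends on which one holds.

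**A reader might infer that the seven-point grid conflicts with the sampling schedule**, since it ends at 120 minutes and the two insulin steps together last 240. The documents do not support that. They list no sampling times to conflict with, and the grid fits a single 2-hour step. All that can be said is that its source is not given.

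**A reader might also infer that insulin sensitivity has only 36% power, or a detectable difference of 1.06 SD where the plan promises 0.61.** That comparison mixes units. The 0.61 is in SDs of a single reading; the 1.06 is in SDs of a per-woman summary. The 36% comes from giving the summary the same SD as one reading, which nothing in the documents supports. Like for like, the target is 0.94 against 1.06 two-sided or 0.93 one-sided, so the shortfall is the sidedness question again. Nor do the documents say that insulin sensitivity is one value per woman. Aim 1 measures it with a clamp combined with labelled glucose, so it may be analysed through the glucose turnover rates in the mixed model.

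**The study is partly a pilot.** This is true and softens the consequence. But the other stated goal is to determine whether lactation changes insulin sensitivity in women as it does in mice, and the protocol uses the 80% to justify its size.

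**Conclusion.** The concern holds for the power figure. With 15 per group, 0.6 between neighbouring values and comparison of the seven-value mean, two-sided power at 0.61 SD is about 70% (72-75% with GLS weights or the normal formula), and 80% power needs about 0.69 SD. The stated 80% corresponds to a one-sided test that is declared nowhere, or to an unstated lag of about 12 minutes or less.

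The conclusion rests on one inference, that the seven-value mean is compared, and on the usual readings of AR(1) correlation and of alpha. It does not show that the study is too small or that its schedule is inconsistent. The missing endpoint, gap and source of the grid are missing detail on their own; they matter here because the power figure cannot be interpreted without them. That insulin sensitivity has no power figure of its own is plain from the text; any number for it is conditional on how it is summarised.

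**What to change.** Keep 32 women and amend the power statement in Section I, item 13 in one of three ways, whichever matches the calculation that was intended:

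- **Two-sided, 0.6 between neighbouring values:** restate as about 70% power at 0.61 SD, or 80% power at 0.69 SD.
- **One-sided:** declare the test one-sided and keep 80% at 0.61 SD.
- **Two-sided with a shorter lag:** state the lag in minutes to which the 0.6 applies and keep 80%, if that lag supports it.

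In each case name the endpoint and the summary compared, and say where the seven times fall. If insulin sensitivity is to be analysed as one value per woman, add that 15 per group detect 1.06 between-woman SD of that summary with 80% two-sided power (0.93 one-sided). Do not set this beside 0.61 without converting units.

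The cost is protocol wording only: no added women, procedures or analyses. The downside is a slightly less favourable stated power or detectable difference.
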